14. STUDY ADMINISTRATION

An overview of the organizational structure is presented below in Figure 1.

14.6. Role of NHLBI

The NHLBI project officer will appoint a Project Scientist who will participate actively in study leadership in conjunction with the CCC and DCC PI, and Site Investigators. The project officer will participate in final protocol and site approvals, monitoring study progress, attend and participate in meetings of the Executive Committee, Steering Committee, and DSMB.

14.7. Executive Committee

The executive committee is the decision and policy making body of the study with oversight in the day to day activities and overall direction of COMPARE-VOE. The EC will review and have final sign-off on the study protocol, manual of operations (MoP), risk-based monitoring plan, approval of final study sites, all site materials, data management plan and statistical analysis plan (SAS). On issues regarding a vote, one vote per member will be allowed. The committee will meet at least once per year in person at the annual NHLBI Sickle Cell Disease research meetings in August or as designated by NHLBI. The committee will be composed of the chair of the COMPARE-VOE Steering Committee, the NHLBI Project Scientist/ Program Official/Scientific Advisor and the principal investigator of the DCC. This group will convene bi-weekly by teleconference alternating with the Steering Committee calls.

14.8. Steering Committee

The Steering Committee will include the CCC and DCC PIs, a SCD hematologist, an ED physician, the six study site Co-I's, as well as the NHLBI Project Scientist/Program Official/Scientific Advisor. [name] (CCC PI) will serve as the Chair, and [name] as Co-Chair. The Steering Committee will assume overall responsibility for all aspects of COMPARE-VOE, including the design and conduct of the studies, quality control, data analysis, and publications. Other supporting committee's from the CCC will report to the SC. The SC will meet monthly and will occur by webinar. The COMPARE-VOE SC will meet face-to-face at a scheduled time during the yearly investigator meetings held annually at Duke; this meeting will not conflict with other agenda items. The steering committee will provide clinical oversight and review side effect data on a monthly basis. The SC will develop a publication plan including specific papers, journals, and authorship criteria. Each member has one vote on the COMPARE-VOE Steering Committee and decisions will be determined by a majority vote.

14.9. Recruitment and Study Coordination Committee

The role of this committee is to monitor recruitment and study site data collection. Specifically, this group will report and discuss recruitment progress and challenges, as well as progress and challenges with data collection during ED visits. This committee consists of all study site project coordinators, study monitors and project coordinator at the CCC. The site coordinators have enormous responsibility for the smooth operation of the project. Each site investigator will be asked to lead this committee for 6-9 months throughout the length of the project. The committee will bring any operational issues to the Steering Committee and implement decisions by the Steering Committee. They will begin meeting in year 1 approximately 3 months before enrollment begins and will meet at least monthly. Either [name] or [name] will also attend these meetings.

14.10. Pain Management Protocols, Clinical Oversight and Implementation Committee

The purpose of this committee is to 1) finalize the pain management protocol, 2) develop the pain management protocol training for site hematologists and ED physicians and nurses and 3) provide clinical oversight during implementation. The committee will meet bi-monthly until the study protocol is finalized and monthly thereafter. A designated ED nurse (see LOS) at each site will participate in these meetings and lead the training of the

nursing staff at each site. The committee will bring any operational issues to the Steering Committee and implement decisions by the Steering Committee.

14.11. DSMB

A DSMB will be appointed by the NHLBI in collaboration with [name] for the COMPARE-VOE trial. The DSMB will be to monitor patient safety and review the performance of the study. The DSMB will be responsible for providing recommendations regarding trial's conduct and guidance to ensure the safety and well-being of participating patients. The composition of the DSMB will be specified in the overall DSMB Charter for the study.

14.12. Committee Meeting Management

The Project Coordinator for the CCC will be responsible to schedule, coordinate, record, and distribute agendas and minutes from all meetings including the Executive Committee, Steering Committee, Recruitment and Study Coordination, and Pain Management Protocols and Oversight Committees. Responsibility will include identification of optimal meeting times and a web-based meeting platform including a conference call number and ability to view and share a computer screen. For in-person meetings the Project Coordinator will find the venue, reserve meeting rooms and audio-visual equipment, develop and circulate agendas, and distribute and archive meeting minutes

15. ETHICS AND GOOD CLINICAL PRACTICE

This study must be carried out in compliance with the study protocol. These procedures are designed to ensure adherence to Good Clinical Practice, as described in the following documents:

ICH Harmonized Tripartite Guidelines for Good Clinical Practice (ICH E6) 1996.
US 21 Code of Federal Regulations Title 45 Part 46 Protection of Human Subjects dealing with clinical studies (including parts 50 and 56 concerning informed consent and IRB regulations).

Participating investigators agree to adhere to the instructions and procedures described in the study protocol. This study protocol was designed to conform to principles of Good Clinical Practice and investigators agree to adhere to these principles.

Treatment Regimen	1:1 treatment allocation will be used with site as the stratification variable. Subjects will be randomized to receive analgesic management for VOE either via a weight-based SCD analgesic, or a patient-specific analgesic developed by their primary SCD outpatient provider.
Blinding	The provider is unblinded in the ED. The patient and research assistants are blinded to study arm.
Objectives:	This phase III randomized clinical trial will identify the best analgesic approach for treating adult SCD patients with VOE during an ED visit. It will determine whether the patient-specific analgesic approach is superior to the weight-based analgesic approach in decreasing the severe pain due to VOE. The trial's results will shape the health care paradigm for the thousands of SCD patients suffering from severe pain.
Primary Endpoint:	Change in pain scores in the ED from the time of placement in treatment area to the time of disposition (hospital admission, discharged home or assigned to observation status) or a maximum treatment duration of 6 hours, whichever comes first
Secondary Endpoints:	
 • ED length of stay • Hospitalization for pain control • Return ED visits • Hospitalizations, if not admitted to hospital on ED visits • Re-hospitalizations, if admitted to hospital on ED visit and was discharged – we ignore those still hospitalized within 7 days of the index ED visits • Day hospital visits, regardless admitted to hospital on ED visits or not • A composite of return ED revisits or hospital re-admissions or day hospital visits (binary outcome with a cutoff at zero)

Location:	6 clinical sites (Emergency Departments (ED)) in the United States
Duration of Treatment	From the time of placement in a treatment area to the time of disposition (hospital admission, discharged home, assigned to observation status) or a maximum treatment duration of 6 hours, whichever comes first.
Duration of Study Overall	The study duration is from the time of placement in a treatment area to Day 7 Post ED Visit. The study enrollment is expected to be 24 months.

ABBREVIATIONS

ACS	Acute Chest Syndrome
ACEP	American College of Emergency Physicians
AE	Adverse Event
CCC	Clinical Coordinating Center
CRF	Case Report Form
DCC	Data Coordinating Center
ED	Emergency Department
EDC	Electronic Data Capture
EMR	Electronic Medical Record
ITT	Intent To Treat
KG	Kilogram
NHLBI	National Heart, Lung and Blood Institute
PI	Principal Investigator
SAE	Serious Adverse Event
SAP	Statistical Analysis Plan
SCD	Sickle Cell Disease
SD	Standard Deviation
SpO2	Peripheral Saturation of Oxygen
VOE	Vaso-Occlusive Episode

Part I

Introduction

1. INTRODUCTION

This document is the statistical analysis plan (SAP) describing data summaries and analyses for the final report of this study, a comparison of individualized vs. weight-based protocols to treat vaso-occlusive episodes in sickle cell disease. Production of data summaries and analyses described in this SAP will be the responsibility of the Data Coordinating Center (DCC).

The reader of this Statistical Analysis Plan is encouraged to refer to the study protocol for details on the conduct of this study, the operational aspects of clinical assessments, and the timing for completing the participation of a patient in this study. This Statistical Analysis Plan is intended to provide guidance to the generation and presentation of the final statistical report.

2. OVERVIEW OF TRIAL DESIGN

This section summarizes the basic trial design, treatment arms, blinding, planned sample size, and randomization scheme.

2.1. Basic Study Design

A multi-site Phase III, single blinded, randomized clinical trial will be conducted to address the study aims. The trial will be conducted at six U.S. sites, with an enrollment period of 24 months. Approximately 460 patients will be consented and randomized in order to obtain the study population of 230 patients with at least one ED visit (from Section 4 of the protocol). The modified intent to treat (ITT) population is adult SCD patients with an ED visit due to VOE.

2.2. Treatment Arms

This will be a single-blinded two-arm randomized clinical trial comparing:

- Patient-specific analgesic protocol to treat VOE in adults with SCD
- Weight-based analgesic protocol to treat VOE in adults with SCD

There is currently no standard approach to managing VOE pain in the ED, resulting in wide variability in ED-based pain management. Patients will be randomized to either a patient-specific analgesic protocol or a weight-based analgesic protocol to treat VOE during an ED visit. (section 6 of the protocol)

2.3. Blinding

The patient hematologist will be un-blinded to the analgesic protocol and will write the treatment plan based on the randomized assigned analgesic protocol to be uploaded in uploaded to the electronic medical record (EMR). However, the emergency physician will be blinded to the analgesic protocol at the time of the patient visit to the ED.

Patients will be told what drug and dose they are receiving during their study ED visit. However, they will remain blinded to the analgesic protocol to which they are randomized. The research assistant performing the study assessments will also remain blinded to the randomized analgesic treatment protocol until all assessments have been completed. (section 6)

2.4. Planned Sample Size

A sample size of 230 subjects with ED visits provides 90% power to detect a 14-mm clinically significant reduction in pain scores for the patient-specific analgesic protocol versus the weight-based analgesic protocol with a 0.05 type I error using a horizontal Visual Analogue Scale 100 mm in length. This assumes the same standard deviation (SD) of 31 mm in pain score reductions in the two groups while accounting for 10%

missing data rate. (section 13)

2.5. Randomization

After patients have provided informed written consent, they will be randomized to either the weight-based analgesic protocol or a patient-specific analgesic protocol that will be developed by their hematologist/sickle cell team. A 1:1 treatment allocation will be used with site as the stratification variable. A computer-generated permuted block randomization schedule with stratification by clinical site will be prepared by the DCC senior statistician with block size randomly chosen that will not be revealed to investigators. This scheme provides chronological balance during enrollment with respect to the number of patients allocated to each treatment arm, and thus balances the treatment groups with respect to possible changes in the mix of patients over time. For the sites, the randomization will be available through the password protected and customized web-based electronic data capture (EDC) system. The EDC will be maintained by the DCC data management team. Treatment plans can be updated as needed by the hematologist. (section 8)

3. OVERVIEW OF ELIGIBILITY AND PROCEDURES

This section summarizes eligibility criteria, study procedures, dosing regimen and visit schedule. (section 5)

3.1. Eligibility Criteria

The population eligible for randomization consists of adult SCD patients meeting the following Inclusion and Exclusion criteria.

The selection criteria below were designed to be inclusive and representative of the SCD population, including appropriate representation of women.

3.1.1. Inclusion Criteria

- 1) \geq 18 years of age
- 2) SCD patients with the following genotypes:
 - a. Hgb SS, SC and SB+, SB- thalassemia

3.1.2. Exclusion Criteria

- 1) Patients with sickle cell trait
- 2) Patients with a treatment protocol that does not allow administration of opioids
- 3) Patients with an existing ED protocol that includes oral opioids only
- 4) Patients prescribed buprenorphine-containing medication in the outpatient setting
- 5) Patients prescribed methadone

The enrolled population will consist of eligible patients meeting the following criteria.

3.1.3. Enrollment Inclusion Criteria:

- 1) Patient is randomized
- 2) ED visit for VOE requiring parenteral opioid analgesia

3.1.4. Enrollment Exclusion Criteria

Patients presenting to the ED with other complications (e.g., acute chest pain, stroke, sepsis, priapism and other pulmonary complications) not clinically appropriate/stable for inclusion

3.2. Study Procedures / Blinding

When the randomized patient has an ED visit for VOE, this patient is enrolled in the

study population. The provider (un-blinded) in the ED will access the patient's randomized analgesic protocol from the EMR for treatment. The patient will only be told what drugs and doses they will receive, but will not be told which analgesic protocol (weight-based or patient-specific) to which they have been randomized, thus the patient is blinded to the randomized arm. Research assistants (RAs), who are also blinded to study arm, will interview the patient during an ED visit to obtain pain score data for the primary outcome. Only one ED visit per patient is recorded for the primary and secondary outcomes. The study is complete as soon as one post-randomization ED visit is recorded and 7-day post ED data are extracted from medical records. The patient's randomized analgesic protocol will be removed from the EMR after the study ED visit is recorded. In the event where the ED visit is missed due to no availability of a RA (e.g., in the middle of the night), the next ED visit will be recorded. The RA will periodically review the EMR to obtain information on the missed ED visits for tracking purposes. During the ED visit, the maximum amount of time for study participation is six hours, which begins at placement in an ED treatment area. A brief interview will be conducted every 30 minutes until 1) discharge home, 2) admission to the hospital or assigned to observation status for continued pain management, or 3) after six hours of treatment (maximum data collection period), whichever comes first. Each patient will be allowed to contribute only one ED visit to the study data. (section 9 of the protocol)

3.3. Schedule of Assessment (section 18)

	Screening/ Enrollment Randomization	ED Visit	Day 7 Post ED Visit
Informed Consent (Site study staff)	X		
Inclusion/exclusion criteria confirmed	X	X	
Pain evaluation questions		X	
ED medication administration; Recording on names of drugs, doses and timing of administration.		x	
AE		X	
SAE		X	X
Return ED visits			X
Hospitalizations			X
Day Hospital Visits			X

4. ENDPOINTS

4.1. Primary Endpoint and Hypothesis

The Primary Endpoint of the study population is the change in pain scores from the time of placement in a treatment area to the time of disposition (hospital admission, discharged home, assigned to observation status) or a maximum treatment duration of 6 hours, whichever comes first.

The Primary Hypothesis of the study population is that the patient-specific analgesic protocol is superior to the weight-based analgesic protocol. (section 11 of the protocol). The sample size of 230 subjects with ED visits provides 90% power to detect 14-mm clinically significant assumptions of the same standard deviations (SD) of 31 mm in pain score reductions in the two groups while accounting for 10% missing data rate.

Method of the Final Analysis will be linear regression used to test the primary hypothesis with pain score reduction (0-100mm) as the dependent variable and treatment indicator with pain score at arrival, biological variables of SCD genotype, age and gender as covariates (independent variables). The primary analysis for hypothesis-testing will be done on the observed data without imputation and without regard to the proportion of missing cases. Summaries of the p-value, 95% confidence intervals and the difference in outcome between the two arms, as well as outcome in each arm will also be computed and presented in tabular and graphic format.

Details will be presented later (section 7 of the SAP).

Missing Data and Sensitivity Analyses of the Primary Endpoint: If more than 5% of randomized patients have the pain score reduction missing, we will use multiple imputations in a **sensitivity analysis**, which would be considered supportive if it gave results consistent in direction and magnitude with the primary analysis. Highly inconsistent results would require further review of how and why the data were missing and suggest concerns with study conduct. This analysis is valid under the missing at random (MAR) assumption. First, an imputation model via linear regression will be developed (based on available data) relating the pain score reduction with a collection of covariates including initial pain score, treatment indicator, baseline characteristics, and possible interactions of covariates with treatment. A total of 1000 data sets with imputations of pain score reduction utilizing the imputation model will be generated. Each of such data sets will be analyzed with linear regression (as described above), and the combined results comparing two groups will be reported by taking into account of variability due to multiple imputations. In **another potential sensitivity analysis**, we will also consider the best and worst scenarios where the worst scenario is to impute the pain score reduction to be zero for patient-specific analgesic protocol and observed maximum pain reduction for the weight-based analgesic protocol and the reverse is used for the best scenario. (section 13.8. of the protocol)

If fewer than 5% of patients have a missing arrival or discharge pain score evaluation, we will perform the primary analysis on the patients without missing data. Two sensitivity analyses will be done:

- 1.) Worst case, assuming missing discharge pain scores are 0 in the weight-based arm and 100 in the patient-specific arm. Missing arrival scores will be assigned the mean of the study population arrival scores.
- 2.) LOCF – imputing missing discharge scores as the last score recorded on the Q 30-minute assessment prior to discharge. Missing arrival scores will be assumed to take the value of the first score recorded on the Q 30-minute assessment. {Although LOCF is in general not a recommended technique, it could be informative in this situation.} The missingness would be due to lack of assessment resulting from one of the four reasons below, each of which could be informed by the most recent pain score.
 - i. The patient is discharged home
 - ii. The patient is admitted to the hospital
 - iii. The patient is assigned to observation status for continued pain management
 - iv. The patient has received 6 hours of treatment

The best approach to missing data is to obtain complete data collection. Age, gender, and SCD type should be available for all patients. SCD type should be one of: Hgb SS, SC, or SB+, SB0 thalassemia. .

The trial will be closely monitored for missing time of bed placement or missing discharge, or 6 hours, pain scores. The first occurrence of missingness within a center will require explanation from the center and a plan to avoid missing data in subsequent patients.

For patients with dosing deviations, we plan to include them in the primary intent-to-treat analysis and collect all study measurements as planned.

Subgroup Analysis of the Primary Endpoint

We will examine whether the finding for the primary endpoint is similar for all patients, or whether it varies according to the following pre-specified subgroups. These will be assessed via interaction terms between treatment and subgroup categories tested at nominal 0.10 level.

- 1) Clinical site
- 2) Gender
- 3) Age (< 30, \geq 30 years old)
- 4) Genotypes (Hgb SS + SB0 and SC + SB+)
- 5) Route (IV or SC) - this will not be carried out if 90% or more subjects receive the IV route.
- 6) Use (yes/no) of NSAIDS
- 7) Drug administered
- 8) Number of repeated doses

9) Total administered milligrams of drug

These analyses will utilize the regression models with main effects and interactions between the randomized groups and pre-specified subgroup variables.

Details of presentation of results are illustrated in section 7.

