13.8. Analysis of Primary Endpoint

The statistical comparison of the two randomized arms with respect to the primary outcome is comparing the means of the pain score reductions between the two arms. A comparison between two groups will be performed, adjusting for the initial pain score at ED time of placement in a treatment area, biological variables of SCD genotype, age and gender. This analysis will utilize linear regression with pain score reduction as the dependent variable and treatment indicator with pain score at time of placement in a treatment area as covariates (independent variables). Rejection of the null hypothesis stating that coefficient for the treatment indicator is zero will provide evidence for presence of the treatment effect. This comparison will utilize subjects with available measure of the primary outcome. In addition to the statistical hypothesis testing, 95% confidence intervals descriptively summarizing the difference in outcome between the two arms, as well as outcome in each arm will be computed.

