13.11. Analysis of Subgroups

If the data provide evidence of an overall difference in outcome between the randomized arms, we will examine whether the effect is similar for all patients, or whether it varies according to the pre-specified subgroups. We will also explore if treatment effect differs by enrolling clinical sites. These analyses will utilize the regression models with main effects and interactions between the randomized groups and pre-specified subgroup variables. We recognize that in our study the power of interaction tests is low, especially for the site by treatment interaction. Hence, in addition to the formal assessment of randomized group by covariate interactions, effects of the treatments will be calculated and displayed (with 95% CI) for the pre-specified subgroups of patients. These descriptive summaries will be carefully interpreted in conjunction with the formal interaction tests. The following variable are used to pre-specify subgroups in the subgroup analyses: gender, age (< 30 , ≥ 30 years old), genotypes (Hgb SS, SC, SB+, SB-), route (IV or SC), use (yes/no) of NSAIDS, drug administered, number of repeated doses, and total administrated milligrams of drug. In the R34 study, the IV route was administrated in over 95% of subjects. The subgroup analysis by route will not be carried out if 90% or more subjects receive the IV route.

[figure not shown]

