4.2. Secondary Endpoints

The secondary endpoints are as follows:

- ED length of stay
- Hospitalization for pain control
- Return ED visits
- Hospitalizations, if not admitted to hospital on ED visits
- Re-hospitalizations, if admitted to hospital on ED visit and was discharged – we ignore those still hospitalized within 7 days of the index ED visits
- Day hospital visits, regardless admitted to hospital on ED visits or not
- A composite of return ED revisits or hospital re-admissions or day hospital visits (binary outcome with a cutoff at zero)

Methods of the final analyses: For the ED length of stay (from ED admission to discharge), a linear regression analysis similar to the primary outcome will be used to compare the length of stay between the two arms. For the hospital admission rate, chi-square test will be used to compare the admission rates between the two groups. For the count data (e.g., ED re-visits or hospitalizations or re-hospitalizations, or day hospital visits for VOE within 7 days after the recorded ED visit), it will be first evaluated by collapsing the data into a binary outcome with a cut off at zero and a chi-square test or Fisher exact test (if frequency is below 5 or less) to compare the re-admission rates or rate of a returned ED visit between the two groups. If there is sufficient spread in the count data, a Poisson regression approach will be used to test for protocol differences in the count outcome. (section 13.9.)

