7.7. Study Endpoints

7.7.1. Primary Endpoint

As defined in the protocol, the primary endpoint is “change in pain scores from the time of placement in a treatment area to the time of disposition (hospital admission, discharged home, assigned to observation status) or a maximum treatment duration of 6 hours, whichever comes first.” Comparison of mean changes in pain scores and the difference between treatment arms will be done using linear regression, adjusting for the initial pain score at ED arrival, biological variables of SCD genotype, age and gender. Comparison of unadjusted means will also be done using a t-test. P-value, 95% confidence intervals and the mean difference will be displayed in tabular format. The predicted values will be displayed in a scatter plot by treatment.

Descriptive statistics such as n, mean, standard deviation (SD), median, 25th and 75th percentiles will be also presented for the primary endpoint.

For subgroup analysis of the primary endpoint, in addition to the formal assessment of randomized group by covariate interactions as described in section 4, effects of the treatments will be calculated and displayed (with 95% CI and p-values) for the pre-specified subgroups of patients in both tabular and graphic format. These descriptive summaries will be carefully interpreted in conjunction with the formal interaction tests.

Please refer to section 4 for methods of analysis.

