17.3. Subgroup Analysis of the Primary Endpoint

	Treatment A N=	Treatment B N=	Estimate (95% CIs), SD	P-value
Gender				
Male				
Female				
Age				
< 30				
≥30				
Genotypes				
SS + SB-				
SC + SB+				
Route				
IV				
SC				
NSAID				
Yes				
No				
Drug Administered				
Yes				
No				
Number of Repeated Doses				
Total Administered Milligrams of Drug

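### Randomization is stratified by site alone, but the primary regression leaves site out; adding it is a cheap, conditional gain in precision, and the planned test is valid without it

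*SAP*

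**What the plan says.** On allocation, SAP 2.5 states: "A 1:1 treatment allocation will be used with site as the stratification variable". Protocol 8.2 says the same and describes permuted blocks within each of six sites. No other stratification factor is named.

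The primary regression is set out in three places, none of which includes site:

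- SAP 4.1: "treatment indicator with pain score at arrival, biological variables of SCD genotype, age and gender as covariates (independent variables").
- SAP 7.7.1: "adjusting for the initial pain score at ED arrival, biological variables of SCD genotype, age and gender".
- Protocol 13.8: adjustment for the initial pain score and "biological variables of SCD genotype, age and gender".

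For length of stay, SAP 4.2 specifies "a linear regression analysis similar to the primary outcome will be used to compare the length of stay between the two arms", so the omission carries over.

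Site does appear in the subgroup work. Protocol 13.11 says "We will also explore if treatment effect differs by enrolling clinical sites", and SAP 4.1 lists clinical site first among the subgroups, to be assessed through "interaction terms between treatment and subgroup categories tested at nominal 0.10 level". Those models contain a site main effect as well as the interaction, but they are not the primary test. The SAP 17.3 table shell, headed "Subgroup Analysis of the Primary Endpoint", has no row for site. The imputation model (protocol 13.8, SAP 4.1) refers to baseline characteristics in general and does not say whether site is among them.

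No reason is given for leaving site out of the primary model, and no sensitivity analysis adds it.

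**The concern.** When randomization is stratified on a factor, the usual practice is to put that factor in the analysis model. If it predicts outcome and is left out, between-site variation stays in the residual and the confidence interval is wider than it need be. With full follow-up the blocking also makes the unadjusted standard error too large, so the test becomes conservative.

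Blocking gives less protection than usual here. Patients are randomized before the ED visit, about half are expected to have one, and 10% of those may lack the outcome. Roughly 45% of each block is therefore analysed, and within-site balance in the modified ITT population is no longer secured. The resulting imbalance is chance variation, not bias, provided that being analysed does not depend on arm.

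Sites could plausibly differ: both documents describe ED pain management as widely variable, and local sickle cell providers choose the agent and write the plan. That makes a site effect credible but does not measure it. The stakes are a modest amount of precision, plus having the covariate set settled before anyone sees results by arm.

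**Working it through.** **Inputs from the documents.** Difference 14 mm; SD 31 mm in each arm; two-sided 0.05; 230 patients with an ED visit; 10% missing; 50% of 460 randomized have a visit (protocol 13.6 and 13.7); six sites, 1:1 within site (protocol 8.2, SAP 2.1 and 2.5).

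**Assumptions not in the documents.** The share of outcome variance lying between sites (written *r*, varied from 0 to 15%); site sizes of 28/22/18/14/10/8%; blocks of 4 or 6; in the covariate runs, initial pain explaining 15% of variance.

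**Step 1: reproduce the stated power.** Analysable n = 230 × 0.9 = 207, or 103.5 per arm.

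SE = 31 × √(2/103.5) = 4.31 mm. 14/4.31 = 3.25, and Φ(3.25 − 1.96) = 90.1%. The noncentral t with 205 df gives 89.9%. The plan's 90% is correct and does not rely on site adjustment.

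**Step 2: what a site term does.** It cuts the residual variance to 31²(1 − r). It costs 5 df and pays for the residual treatment-by-site imbalance, which raised variance by about 1.4% in simulated allocations with 45% of patients analysed. So

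SE with site ≈ 4.31 × √[(1 − r) × 1.014].

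On this formula the SE breaks even where (1 − r) × 1.014 = 1, at r ≈ 1.4%. Noncentral t with 200 df then gives the power:

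| r | SE with site (mm) | Power with site | Power without site |
|---|---|---|---|
| 0% | 4.34 | 89.4% | 89.9% |
| 2% | 4.30 | 90.0% | 89.9% |
| 5% | 4.23 | 90.9% | 89.9% |
| 10% | 4.12 | 92.3% | 89.9% |
| 15% | 4.00 | 93.6% | 89.9% |

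**Step 3: simulation, treatment with or without site.** 8,000 trials per setting: 460 randomized, each analysed with probability 0.45, total SD 31. The Monte Carlo SE of the power difference is 0.1 to 0.2 point.

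| r | Power without → with site | Change (points) | Mean model SE (mm) | Type I error without site |
|---|---|---|---|---|
| 0% | 89.8 → 89.4 | −0.5 (unrounded difference) | not tabulated | 5.1% |
| 2% | not tabulated | +0.3 | not tabulated | 4.9% |
| 5% | 90.1 → 90.8 | +0.7 | 4.31 → 4.23 | 4.7% |
| 10% | 89.7 → 91.9 | +2.2 | 4.32 → 4.12 | 4.8% |
| 15% | 90.6 → 93.7 | +3.1 | 4.32 → 4.01 | 4.3% |

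Bias without site was under 0.03 mm. The empirical SD of the no-site estimate was 4.28, 4.27 and 4.15 mm at 5, 10 and 15%. It falls clearly below the model SE only at 15%, which is where the test becomes slightly conservative. Separate runs with equal and unequal sites, and *r* from 0 to 20%, gave type I error without site of 4.0 to 5.2% (Monte Carlo SE about 0.4 point), so there is no inflation.

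**Step 4: simulation with the planned covariates in both models.** This is closest to the real plan. Change in power from adding site:

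| r | First set (6,000 trials per setting) | Second set |
|---|---|---|
| 0% | −0.3 | −0.7 |
| 2% | not run | +0.1 |
| 5% | +1.1 | +0.7 |
| 10% | +1.8 | +1.8 |

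If half of the site difference acts through initial pain, which is already in the model, the gain falls to +0.2 at 5% and +0.8 at 10%.

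**Step 5: the confidence interval.** At r = 5% the 95% half-width goes from 1.972 × 4.31 = 8.50 mm to 1.972 × 4.23 = 8.34 mm. At 10% it goes from 1.972 × 4.32 = 8.52 mm to 1.972 × 4.12 = 8.12 mm.

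**The case against.** The case against is that nothing here is broken. The trial was sized on an unadjusted t-test, the covariate set is the same wherever it is listed, and the test is valid as planned. The benefit depends on a between-site variance that nobody has stated. The larger figures (+2.2, +3.1) come from a model without the planned covariates; in the model that will be fitted, a 5% site share is worth about one point, or as little as +0.2, which is within simulation error of zero. The plan's own Table 4 already spans 85 to 92% power, and the blinded sample size re-estimation would react to a larger pooled SD, which includes variation between sites. A site main effect is also already specified in the subgroup models.

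Most of this stands and limits the claim. It rules out any suggestion of bias or a wrong power statement, and it makes the covariate-adjusted figures the ones to quote. Three points remain. The site main effect in the subgroup models does not change the primary test. The re-estimation would recover power by recruiting more patients, whereas a site term might recover some of it without them. And the trade is favourable on balance: a loss of 0.3 to 0.7 point if sites do not differ, against 0.7 to 1.8 points with the planned covariates if they differ moderately. Where most of the site difference runs through initial pain, gain and cost are about equal and the case rests on consistency with the randomization.

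**Conclusion.** The point holds as one of efficiency and specification. Site is the sole stratification factor and the primary model omits it. The planned analysis remains unbiased, with type I error at or slightly below 5% and the stated 90% power intact. With the planned covariates, adding site is worth roughly +0.7 to +1.1 power points at a 5% between-site share and +1.8 at 10%, less if initial pain absorbs part of the site effect. It costs 0.3 to 0.7 point if sites do not differ, with break-even near a 2% share.

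These figures rest on assumed between-site variance, site sizes and covariate strength, and on being analysed not depending on arm. No gain was computed for length of stay; that change is for consistency with the primary model. The missing site row and the imputation wording are small matters of completeness. The subgroup figure in SAP 12.3 is not visible, so whether site is displayed there cannot be confirmed.

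**What to change.** Before unblinding:

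1. Add site as a fixed effect (five indicator terms) to the primary regression in SAP 4.1 and 7.7.1 and protocol 13.8, and to the length-of-stay regression in SAP 4.2 and protocol 13.9.
2. State a rule for pooling very small sites.
3. Name site among the imputation covariates.
4. Add a site row to the SAP 17.3 table, since SAP 4.1 lists site as a subgroup.

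A site-stratified test for the binary secondary outcomes is optional. If the team prefers to keep site out of the primary model, it should give the reason and could pre-specify the site-adjusted model as a sensitivity analysis.

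The cost is a phrase in each analysis section, one sentence on pooling, one on imputation, and a table row. The model uses five of about 200 degrees of freedom. If sites turn out not to differ, allow for a loss of up to about one power point. No change to sample size or data collection is needed.
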